4.2 Stratification and Randomization

Subjects will be randomized to receive RBCs stored either ≤ 10 days at time of transfusion or ≥ 30 days at the time of transfusion. Storage arm assignment applies to up to 3 consecutive outpatient transfusions, beginning at the time of randomization and continuing through the end of the 3rd randomized outpatient transfusion. Randomization assignment can occur at any time between the date of consent till 2-3 days prior to the first study transfusion. Only the transfusion service will have access to the randomization assignment as designated by the study biostatistician.

Due to the pilot nature of this study, randomization will not be stratified by gender, age, ethnicity, or hemoglobinopathy type.

For the first study transfusion, after the number of units requested for crossmatch is known, but no earlier than 2-3 calendar days before transfusion, a study staff member will contact the institution's transfusion service to determine whether the transfusion service has enough suitable units stored ≤ 10 days and ≥ 30 days to meet the crossmatch request for this subject.

If there is not sufficient inventory to meet the randomization criteria, the subject's study participation will be postponed, and unit availability will be assessed again prior to their next outpatient transfusion.

Once the subject has received their first study transfusion, the remaining 2 outpatient study transfusion events will occur regardless of whether the transfusion service can meet the transfusion needs of the study.

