4.3 Masking of Treatment Allocation

At enrollment, the subject's eligibility status and ABO/Rh type will be entered into the data management system. If eligible, the subject will be randomized at the time of consent, but no later than 2-3 calendar days before the first outpatient study transfusion. Unit age availability will be assessed no earlier than 2-3 calendar days before the first outpatient study transfusion, and the study will commence if unit availability is satisfactory for that subject. The study start will be delayed until the next outpatient transfusion if blood unit availability is deemed insufficient for that first study transfusion. Only blood bank staff with the appropriate security level in the data management system will be able to access the treatment arm assignment. Access to case report forms containing information about the age of the RBC products sent for each subject will also be restricted at the site to the appropriate blood bank staff. Clinical staff overseeing the subject's participation in the trial, collecting data, and reporting the data into the data management system will not have access to the treatment arm assignment or information about the age of the RBC products transfused.

No alteration will be made to the labels on the RBC units. The expiration date, collection date, and any processing dates (e.g. irradiation dates) will not be obscured. Medical infusion clinic personnel physically providing the RBC transfusions will verify product and patient identity according to hospital-specific procedures. These personnel will be instructed to not divulge the patients' randomization assignments. Other infusion clinic staff (other than those actually infusing RBCs), will be instructed not to seek to identify the age of the products the patients are receiving. The subjects themselves will not be informed of their randomization assignment and will also be instructed not to seek to identify the age of the products they are receiving. However, as the key components of this study are objective, inadvertent unblinding of the randomization assignment will not compromise the validity of the study.

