5.1.1 Preparation criteria applying to both treatment arms

The following criteria apply to all study RBC units in both treatment arms. Any study RBC unit which does not meet all these criteria will be considered a protocol violation.

1. Institutional processing standards will be maintained for all units.
2. All study RBC units should be pre-storage leukoreduced.
3. All study RBC units should be stored in either AS1, AS3, or AS5.
4. No study RBC unit should be washed before release from the transfusion service.
5. No study RBC unit should be volume-reduced.
6. No study RBC unit should include a frozen product.
7. No study RBC unit should be deglycerolized.
8. No study RBC unit should be irradiated.

5.1.2 Preparation of RBC units for subjects randomized to receive units stored \leq 10 days

All study RBC units released from the blood bank for subjects randomized to receive units stored \leq 10 days should have been stored \leq 10 days at the time of transfusion.

If there are not enough suitable units stored \leq 10 days at the time a study RBC transfusion is needed, the blood bank should release suitable units with the minimum available storage time. The transfusion itself should not be cancelled or postponed because there are not enough suitable units stored \leq 10 days.

Study units stored longer than 10 days will be considered protocol deviations for subjects in this treatment arm if used for an outpatient transfusion and after the first successful randomization.

Subjects randomized to this treatment arm are likely to receive units with shorter storage times than the units they would receive if not in the study, but this is not guaranteed to be true for any particular subject.

5.1.3 Preparation of RBC units for subjects randomized to receive units stored \geq 30 days

All study RBC units released from the blood bank for subjects randomized to receive units stored \geq 30 days should have been stored \geq 30 days at the time of transfusion.

If there are not enough suitable units stored \geq 30 days at the time a study RBC transfusion is needed, the blood bank should release suitable units with the maximum available storage time. The transfusion should not be cancelled or postponed because there are not enough suitable units stored \geq 30 days.

Units stored less than 30 days will be considered protocol deviations for subjects in this treatment arm.

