6. SCHEDULE OF MEASUREMENTS

6.1 Red Cell Unit Sample Collection:

2 ml blood from each donor unit will be obtained from 6 sterile unit links/segments on the day of the 3 randomized outpatient transfusion events. PE and PS exposure, and microparticles, will be measured by flow cytometry using the LSR2-green, and all flow analyses will be recorded using FACSDiVa software. The plasma fraction from each red cell unit will be diverted to EPR (Bruker Elexys X-band system, Billerica, MA, USA), a Bio-Plex cytokine assay kit (Bio-Rad Laboratories), and a fluorescent immunoassay (DxFerr kit) to quantify concentrations of free heme/hemoglobin, cytokines (IL-1, IL-6, IL-8, MCP-1), and NTBI, respectively.

6.2 Patient Sample Collection (Table 1):

A. One - *four weeks prior to the first transfusion*:

- 15ml whole blood for flow cytometry and EPR measurements

B. *Immediately prior to each red cell transfusion*:

- 15ml whole blood for flow cytometry and EPR measurements
- 15ml to McLendon Labs
- blood culture to McLendon Labs (8-10ml blood/culture bottle)
- urine to McLendon Labs (12 ml urine)

C. *Two hours after each red cell transfusion (1 ½- 3 hours)*

- 15ml whole blood for flow cytometry and EPR measurements
- 15ml to McLendon Labs

D. *1 day after each red cell transfusion (about 21-27 hours after)*

- 15ml whole blood for flow cytometry and EPR measurements
- 15ml to McLendon Labs

E. *2 weeks after each red cell transfusion (+/- 2 days)*

- 10ml McLendon Labs

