The primary outcome measure is the change in CD62L (activated) circulating monocyte/macrophage MFI at 2 hours post-transfusion compared to the subject pre-transfusion. We will compare the two groups (\geq 30 day-old compared to \leq 10 day-old unit exposure) using a two sample two-sided t-test of the log at an alpha of 0.05. Power: We will have at least 80% power to detect a change in the ratio of 1.35 post-transfusion if the variability is similar to that seen in our preliminary data.

Exploratory: We will use a general(ized) linear model to include biochemically old units transfused (Aim 1 outcome), regardless of unit age, as a covariate in our analysis. Other co-variates in this model will include free heme, cell free hemoglobin, and NTBI. We will similarly compare other obtained activation measures as outcomes: activation markers for monocytes, neutrophils (as listed in section 6) and measured plasma cytokine

concentrations (section 6). We will also plan for auxiliary analyses of the outcome variables in which the explanatory variable is the age (days) of the RBC units --to characterize the degree to which age (days) can accurately predict the clinical and physiologic outcome measures defined. Lastly, as an exploratory aim, we will evaluate the *in vivo* change in recipient red cell PE/PS positivity at 2 and 24 hours post transfusion.

Aim 3:

The primary outcome variable is the rate of post-transfusion infections in the patient. The primary estimand is the treatment effect defined as the difference between the regimen-specific proportions of patients in the target populations that would experience post-transfusion infections. This population parameter will be estimated as a function of the proportions observed in the sample of patients studied. The point estimate will be reported along with the corresponding 95% confidence interval estimate. The presence of an indwelling catheter will be used as a key co-variate in this analysis. *Power:* A difference of 20% will be of clinical interest. We do not expect to have adequate power for this pilot study but at an alpha of 0.05 with 20 subjects in each group we will be able to detect a difference of 47% between the proportions.

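### Aim 2's primary t-test takes one CD62L value per patient, but each patient yields up to three pre/2-hour pairs, and the test is not reconciled with the plan's repeated-measures and off-age rules

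*Combined protocol and SAP*

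**What the plan says.** Section 10.2.1 (Aim 2) takes as primary outcome the change in monocyte/macrophage CD62L MFI from before transfusion to 2 hours after. It compares the arms "using a two sample two-sided t-test of the log at an alpha of 0.05". Section 2.1 states 80% power with 40 patients for an MFI ratio of 1.35; section 10.2.1 says at least 80%, provided the variability matches the preliminary data.

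The sampling is repeated. Section 4.2: "Storage arm assignment applies to up to 3 consecutive outpatient transfusions". Section 6.2 takes flow cytometry blood at item B, "Immediately prior to each red cell transfusion", and at item C, "Two hours after each red cell transfusion". Table 1 shows the same schedule.

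The three transfusions are not alike in supply. For the first, section 4.3 says: "The study start will be delayed until the next outpatient transfusion if blood unit availability is deemed insufficient for that first study transfusion". After that, section 4.2 says: "the remaining 2 outpatient study transfusion events will occur regardless of whether the transfusion service can meet the transfusion needs of the study". In the older arm, when stock is short, section 5.1.3 says "the blood bank should release suitable units with the maximum available storage time", and also that "Units stored less than 30 days will be considered protocol deviations for subjects in this treatment arm". Section 5.1.2 has a matching rule for the younger arm.

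Section 10.2 adds two relevant rules. Transfusion events with off-age units are left out of a subanalysis that sits beside the ITT analysis. Under missing data, and assuming data are missing at random, repeated measures are to be handled by a random effects model.

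On the scale, the key-variable list in section 10.2.1 defines CD62L as the percentage of monocytes that are positive. The Aim 2 outcome and both power statements use MFI. The Aim 2 hypothesis in section 2.1 speaks of a number of cells.

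**The concern.** A two-sample t-test powered on 40 patients needs one independent value from each. The schedule yields up to three, and no sentence says which one enters the test or how they are combined. Dropping off-age events from a subanalysis only makes sense if later events are in the main dataset, because the first transfusion is held back until stock is adequate. So section 10.2 leans towards using all events, while the test in section 10.2.1 has no place for them.

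The choice affects both precision and meaning. A first-event analysis has the best-controlled age contrast and the least information. An all-event analysis by randomised arm has more information, but it averages over transfusions that may use off-age units. Entering every event as a separate observation would fit the words of the t-test but ignore within-patient correlation. Section 2.1 says the results will inform a larger trial, and an SD is of little use for that unless readers know whether it describes one event or a patient mean.

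**Working it through.** **Inputs from the documents.** Two-sided alpha 0.05, two-sample t-test on the log scale and a ratio of 1.35 (section 10.2.1, Aim 2); 40 patients (section 2.1); 20 per group (stated under Aim 1); up to three events (section 4.2).

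**Not in the documents.** The SD of the log ratio, and the within-patient correlation rho of log ratios between events. The preliminary CD62L result (a 34% rise in 8 transfused adults) is at 24 hours and has no SD.

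**Step 1: the plan's own figure.** It cannot be reproduced without an SD, so I solve backwards. With 20 per arm (38 df), 80% power needs a standardised difference of 0.909.

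ln(1.35) = 0.300, so SD = 0.300 / 0.909 = 0.330.

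Because section 10.2.1 says at least 80%, this is the largest SD consistent with the claim. With an SD of 0.30, 0.40 or 0.50, power would be 87%, 64% or 46%.

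**Step 2: one event or a patient mean.** Take 0.330 as the SD for one event (assumption). A mean of k events has variance 0.330² × (1 + (k − 1)rho) / k. With 20 per arm and no baseline adjustment:

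| Value per patient | rho | Variance factor | Power at 1.35 | Ratio detectable with 80% power |
|---|---|---|---|---|
| One event | – | 1 | 80% | 1.35 |
| Mean of 2 | 0.3 / 0.5 / 0.7 | 0.65 / 0.75 / 0.85 | 94 / 90 / 86% | 1.27 / 1.30 / 1.32 |
| Mean of 3 | 0.3 / 0.5 / 0.7 | 0.533 / 0.667 / 0.800 | 97 / 93 / 88% | 1.25 / 1.28 / 1.31 |

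If 10% of patients have one event, 10% two and 80% three (assumed), simulation of the patient-mean t-test (20,000 runs) gives power of 95, 92 and 87% at the three correlations, with type I error close to 5%.

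**Step 3: pooling events as independent.** Simulating 60 v 60 values under no effect (20,000 runs), the nominal 5% test rejects in about 10% of trials at rho 0.2, 17% at 0.5 and 24% at 0.8.

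**Step 4: how much dilution the gain can bear.** Step 2 assumes the full age contrast at transfusions 2 and 3. Suppose only a fraction f of the log effect remains there. The three-event mean then has effect ln(1.35) × (1 + 2f) / 3. It matches the first event alone when (1 + 2f) / 3 equals the square root of the variance factor:

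- rho 0.3: √0.533 = 0.730, so f = (3 × 0.730 − 1) / 2 = 0.60
- rho 0.5: √0.667 = 0.816, so f = 0.72
- rho 0.7: √0.800 = 0.894, so f = 0.84

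So the three-event mean has more power as long as later transfusions keep, on average, more than about 60 to 84% of the effect. The documents give no off-age share, so f is unknown. Releasing the closest available age would keep part of it.

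**The case against.** The strongest reply is that section 10.2 already covers this: it names a random effects model for repeated measures, and its subanalysis without off-age events shows that all events are meant to be used and that the contrast problem was foreseen. Much of that stands. A reader might infer that the plan is silent on repeated measures, or that first-event and all-event analyses fit it equally well; section 10.2 supports neither. But the random effects clause sits under missing data, is not tied to Aim 2 and is a different analysis from the named t-test. The subanalysis is described by summaries, plots and tree analysis, and gives no rule for combining events.

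A second reply is that the illustration shows no harm, since power is at or near 80% in each valid scenario and section 2.1 calls this a feasibility study with preliminary power figures. That also stands: no power shortfall is shown. What remains is precision given up on data already collected, and a literal reading that permits an invalid test.

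On scale, a reader might count three competing definitions of CD62L. The number of cells in section 2.1 is hypothesis wording, and the power sentence beside it uses MFI. The real conflict is the one line in the key-variable list.

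A reader might also infer that the choice of event will be made by someone who knows the arms. Section 6.6 gives the assignments to a designated study statistician, and section 10.2 gives the analysis to the lead biostatistician or a designee. The documents do not say these are the same person.

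**Conclusion.** The point holds as a defect of specification in a primary analysis and should be fixed. The Aim 2 t-test is not reconciled with the repeated sampling, with the random effects clause or with the off-age subanalysis, and the key-variable list conflicts with the outcome on the measure.

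Its size is illustrative: 80% power for one event against 88 to 97% for a three-event mean, or a type I error of about 10 to 24% if events are pooled as independent. The power figures rest on the back-solved SD of 0.33, an assumed correlation of 0.3 to 0.7 and an age contrast that persists at transfusions 2 and 3. The error rates rest on an assumed correlation of 0.2 to 0.8.

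A reader might go further and conclude that the trial is underpowered or its result unsafe. The documents do not support that: they give no SD from which to show a shortfall, and nothing in them says the events will be pooled as independent.

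**What to change.** 1. **Measure.** Make the log ratio of CD62L MFI, 2-hour over same-day pre-transfusion, the sole primary measure for Aim 2. Align the key-variable list in section 10.2.1 and the hypothesis wording in section 2.1 to it.
2. **Primary analysis.** Compare randomised arms using all study transfusions with the patient as the unit: either ANCOVA on each patient's mean log ratio, or an equivalent model with a random patient intercept. Adjust for log MFI before the first study transfusion, and cross-refer the random effects clause in section 10.2 to this analysis.
3. **Supporting analyses.** Report the first transfusion alone as a sensitivity analysis beside the existing subanalysis that excludes off-age events. State that at transfusions 2 and 3 the same-day pre value is taken after randomisation, so the ratio measures the acute response only.

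The cost is wording, with no new samples, visits or patients. This assumes that the 15 subjects already enrolled were sampled on the same schedule. The change should be dated and fixed before CD62L results are compared by arm. The downside is that the ITT average may be diluted by off-age units at transfusions 2 and 3, which the supporting analyses would help to show.

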Trial design: Adults and adolescents (post puberty) with SCD who are treated with outpatient red cell transfusions will be randomized in blocks of 5 (S. Piantadosi block randomization software, 2010) to receive ≥ 30 day or ≤ 10 day old units for 3 months (3 consecutive transfusion events). **The study statistician** will provide the blood bank with the schema who will then be responsible for providing the units for these subjects. Participants and all other investigators will be blinded to treatment assignment.

Two baseline venous blood samples will be obtained to be used as a baseline measurement of the patients underlying inflammatory status. The first will be drawn about 1- week prior to the first randomized transfusion, and the second sample just prior to the first randomized transfusion. Subjects will be asked to hold their iron chelation 72 hours before the study transfusion. Pre-transfusion, sterile samples will be extracted from red cell units. Patient venous blood samples will be also obtained 2 hours post transfusion, 24 hours post-transfusion, and 2 weeks post-transfusion (**Table 1**). Participants will complete standardized diaries daily to document symptoms of infection, SCD pain, medications and emergency department (ED) or hospital use. Diaries will be collected and participants will be assessed with each transfusion encounter, up to 3 transfusion events, and 4 weeks after the last transfusion. To ensure compliance, coordinators will

contact subjects regularly to remind them to complete diaries. All data will be captured with standardized case report forms and entered into an electronic database.

Subject Recruitment and Anticipated Numbers: We intend to recruit and enroll 40 subjects. Participants will be recruited from the Adult SCD Clinic at UNC and Emory/Grady Health System. We expect that UNC will recruit between 5-10 subjects over the next 2 years (15 subjects have already been enrolled at Medical College of Wisconsin), and Emory will recruit between 10-20 subjects to reach the study goal of 40 randomized subjects.

Subject Inclusion/exclusion criteria:

Inclusion criteria:

- 1) Ages 16 to 60 years old
- 2) Subject must have sickle cell anemia confirmed by hemoglobin analysis
- 3) Must be receiving red cell transfusion therapy
- 4) Must be outpatient at the time of study transfusions

Exclusion criteria:

- 1) History of severe reactions to transfusion therapy
- 2) Receive red cell transfusions that are crossmatch incompatible

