2. OBJECTIVES

2.1: Primary Aims

Note: This randomized clinical study should be considered a feasibility study to determine the ability to design and run a protocol of this nature. Each Aim was specifically selected

to maximize the possibility that novel information could be obtained from this trial. However, power calculations and associated precision estimates should be considered preliminary, as the data derived from this study will inform the calculations necessary to design a larger, more definitive study.

Aim 1:

To characterize the physiologic differences between ≥ 30 vs ≤ 10 day-old units. As part of the randomized study, we will measure PS exposure on donor red cells, as well as PE, microparticles, plasma free hemoglobin, heme, and NTBI. We hypothesize that ≥ 30 day-old units will have significantly more **biochemically old units** (see section 10 for the definition) than <10 day-old units. With a total sample size of 40 patients (20 in each group), we will have at least 80% power ($\alpha=0.05$) to detect a difference of at least 47% between the two randomized groups for biochemically old red cell units (close to a 100% difference is expected).

Aim 2:

To quantify whether physiologic differences between ≥ 30 day-old units versus ≤ 10 day-old units promote immune cell activation in transfused adults with SCD. We will perform flow cytometry to measure the activation of monocytes and neutrophils, as well as measure cell-free hemoglobin, heme and NTBI on blood samples before, 2, and 24 hours after transfusion. We hypothesize that those administered ≥ 30 day-old (biochemically old) units will have a greater increase in the number of CD62L + activated monocytes at 2 hours post-transfusion compared to those administered <10 day-old units. With a sample size of 40 patients, we will have 80% power ($\alpha=0.05$) to detect a change in MFI ratio of 1.35.

Aim 3:

To explore whether the physiology of ≥ 30 day-old units versus ≤ 10 day-old units is associated with adverse clinical outcomes in transfused adults with SCD. We will perform a systematic evaluation of hospital admissions, pain scores, medications, and clinical symptoms prior to each transfusion and at the end of the study period (**Table 1**). We hypothesize that reports of infection will be greater in subjects randomized to receive ≥ 30 day-old older units.

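### The Aim 2 primary t-test on log change in CD62L MFI is valid but does not condition on baseline; ANCOVA on the immediate pre-transfusion value would probably gain precision at almost no cost, and the earlier baseline sample has no stated use.

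*Combined protocol and SAP*

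**What the plan says.** Section 10.2.1, Aim 2, defines the endpoint: "The primary outcome measure is the change in CD62L (activated) circulating monocyte/macrophage MFI at 2 hours post-transfusion compared to the subject pre-transfusion". The arms are compared "using a two sample two-sided t-test of the log at an alpha of 0.05". No covariate is named. The exploratory Aim 2 model adds biochemically old units, free heme, cell-free hemoglobin and NTBI, but not baseline CD62L.

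On power, the same section states: "We will have at least 80% power to detect a change in the ratio of 1.35 post-transfusion", conditional on variability: "if the variability is similar to that seen in our preliminary data". Section 2.1 ties this to the total size: "With a sample size of 40 patients, we will have 80% power". Neither the SD nor the correlation between time points is given.

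On baseline sampling, the synopsis (Trial design) states: "Two baseline venous blood samples will be obtained to be used as a baseline measurement of the patients underlying inflammatory status". On timing it adds: "The first will be drawn about 1- week prior to the first randomized transfusion". Section 6.2 A and Table 1 instead allow one to four weeks before the first transfusion (the outer limit in 6.2 reads "four weeks prior to the first transfusion"). Both places schedule flow cytometry on this early sample and on the sample taken just before each transfusion. Section 10 does not mention the early sample.

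**The concern.** A change score gives the baseline a coefficient of exactly 1. When the correlation between baseline and 2-hour values is below 1 and the variances are similar, that coefficient is too large. Part of the noise in the pre-transfusion value is then carried into the outcome, and a chance difference between arms at baseline leaves a trace through regression to the mean. ANCOVA estimates the coefficient from the data. With about 20 patients per arm and unstratified randomization, chance imbalance is quite possible and precision is scarce.

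The early sample is a second matter. Patients give blood for a stated baseline purpose, yet no analysis says how the result enters.

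**Working it through.** **Inputs.** From the documents: ratio 1.35, two-sided alpha 0.05, 80% power, 40 patients. The split of 20 per arm is stated under Aims 1 and 3 and is taken to apply to Aim 2. Assumed: equal variances s² of log MFI at each time point, and the correlation ρ between immediate baseline and 2-hour value.

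**The plan's own figure.** It cannot be reproduced without an SD, so I solve for the SD it needs. The log effect is ln(1.35) = 0.300. With 20 per arm and 38 df, the noncentral t gives 80% power at a standardized difference of 0.909, so SD = 0.300/0.909 = 0.330. For other SDs of log change, the planned test would have:

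| SD | Power |
|---|---|
| 0.30 | 87% |
| 0.35 | 75% |
| 0.40 | 64% |
| 0.50 | 46% |

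**One baseline.**
- Var(change) = 2s²(1−ρ).
- ANCOVA residual variance = s²(1−ρ²).
- Ratio of ANCOVA to change = (1+ρ)/2.
- Estimating the slope multiplies the ANCOVA variance by 1 + 1/36 = 37/36 and leaves 37 df.

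Holding the SD of change at 0.330:

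| ρ (assumed) | (1+ρ)/2 | After slope cost | Effective SD | Power at 1.35 | Ratio detectable at 80% |
|---|---|---|---|---|---|
| 0.4 | 0.70 | 0.719 | 0.280 | 91% | 1.290 |
| 0.5 | 0.75 | 0.771 | 0.290 | 89% | 1.302 |
| 0.7 | 0.85 | 0.874 | 0.309 | 85% | 1.324 |
| 0.8 | 0.90 | 0.925 | 0.317 | 83% | 1.335 |
| 0.9 | 0.95 | 0.976 | 0.326 | 81% | 1.345 |
| 0.95 | 0.975 | 1.002 | 0.330 | 80% | 1.351 |

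The gain vanishes where (1+ρ)/2 × 37/36 = 1, that is at ρ of about 0.945. A simulation of 20,000 trials at each of ρ = 0.5, 0.7 and 0.9 gave 80% for the planned test in every case, and 89%, 85% and 81% for one-baseline ANCOVA.

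**Adding the early sample.** Let r₂ be the immediate–outcome correlation, r₁ early–outcome and r₁₂ early–immediate (all assumed).
- Both entered separately: R² = (r₁² + r₂² − 2r₁r₂r₁₂)/(1 − r₁₂²), variance factor 1 + 2/35 = 37/35, 36 df.
- Mean of the two: R² = ((r₁+r₂)/2)²/((1+r₁₂)/2), factor 37/36, 37 df.

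Worked case 0.7/0.5/0.5: s = 0.330/√(2×0.3) = 0.426.
- Both: R² = (0.25 + 0.49 − 0.35)/0.75 = 0.52; SD = 0.426√(0.48×37/35) = 0.304; power 86%.
- Mean: R² = 0.36/0.75 = 0.48; SD = 0.426√(0.52×37/36) = 0.312; power 84%.
- Immediate only: 85%.

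| r₂/r₁/r₁₂ | Immediate only | Both entered | Mean of both |
|---|---|---|---|
| 0.7/0.5/0.5 | 85% | 86% | 84% |
| 0.8/0.5/0.5 | 83% | 83% | 75% |
| 0.9/0.6/0.6 | 81% | 81% | 62% |
| 0.7/0.7/0.7 | 85% | 90% | 91% |

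A separately entered early sample costs almost nothing when it is weak. Averaging can take power below the planned 80%. The larger gain in the last row needs the early sample to predict as well as the immediate one.

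**The case against.** **The planned test is not wrong.** It is unbiased under randomization, Section 2.1 calls the study a feasibility trial with preliminary power calculations, and Section 10.2 promises sensitivity analyses over variations in method. All of this stands. It makes the point one of efficiency, but an unspecified sensitivity analysis does not prespecify a primary model.

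**A reader might infer that the test ignores baseline.** It does not: the endpoint is a change from the subject's own pre-transfusion value. What is missing is conditioning on that value.

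**A reader might infer that the early sample is excluded.** Section 10 is silent. The synopsis could be read as pooling the two samples, and the precision estimates for CD62L under Aim 5 could use them, although neither is stated.

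**A reader might infer that using both samples would lift power above 90%.** That needs a sample drawn one to four weeks earlier to predict the 2-hour value about as well as one drawn just before transfusion. Nothing in the documents supports this. The same assay hours apart could also correlate at 0.9 or more, where even the one-baseline gain is negligible.

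**Changing the model mid-trial is not free.** Fifteen subjects are already enrolled, and the statistician and DSMB know the allocation (Sections 6.6 and 8.6). This stands and governs when and how the change is made.

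**Conclusion.** The point holds as a worthwhile gain in precision, not as an error of validity. One-baseline ANCOVA would give about 91% to 83% power at a ratio of 1.35, against 80% for the planned test, if ρ lies between 0.4 and 0.8. It adds about 1 point at 0.9 and nothing near 0.95. The algebra is firm. The size rests on an SD inferred from the plan's own power claim, on equal variances, on 20 per arm with no losses, and on a correlation that the documents do not report. The early sample's own contribution is about 1 point at correlations of 0.7/0.5/0.5, and more only if it predicts nearly as well as the immediate sample. The lack of any stated use for it, and the two different sampling windows, are plain gaps in the text.

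**What to change.** 1. Make the Aim 2 primary analysis an ANCOVA of log 2-hour CD62L MFI on arm, with log CD62L MFI taken immediately before that transfusion as covariate. Report the adjusted ratio with a 95% CI. Keep the two-sample t-test on log change as a sensitivity analysis.
2. State which transfusion or transfusions enter the test. For the first study transfusion the covariate precedes all study treatment; for the second and third it does not.
3. State the use of the early sample. Its log CD62L may enter as a separate second covariate. Do not average it with the immediate value. If it is used, say how a missing early sample is handled.
4. Reconcile the early-sample window: about one week in the synopsis, one to four weeks in Section 6.2 and Table 1.
5. Report the SD of log change and the between-time correlation from the preliminary data if available, and from this trial under Aim 5.

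The cost is one or two degrees of freedom and an amendment to the analysis text, with no new samples. The change should be dated and fixed before any unblinded analysis of CD62L.
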